9.1.3.2.1. Vaccination (Days 1, 29, and 57)

Visit 2: Day 1/Day of Randomization/Vaccination 1

After re-check of the inclusion and exclusion criteria,^x abbreviated physical examination (at the discretion of the investigator) and measurement of vital signs, length and weight, eligible subjects will be randomized as described in Section 5. If medical status and/or physical examination suggests significant changes have occurred since screening, either the Day 1 visit can be re-scheduled, or the subject excluded from the study if he/she fails to meet the inclusion and exclusion criteria. Before the first vaccination, the investigator must check for any symptoms of an acute illness or body temperature ≥ 38.0 °C. In such a situation, the subject may be enrolled at a later date^y, or be withdrawn at the discretion of the investigator and after consultation with the sponsor.

Collection of blood samples and nasal samples for baseline immunogenicity assessments can be either at screening or pre-dose on Day 1, at the discretion of the investigator, however both samples should be collected on the same day. If fingerstick sampling for RSV serology is done at screening, blood draw for immunogenicity should be on Day 1.

Administration of first dose of study vaccine.

Subjects will be closely observed for a minimum of 30 minutes (or 60 minutes, depending on local or study-site requirements) post-vaccination to monitor for the development of any acute reactions, or longer if deemed necessary by the investigator. Any unsolicited, solicited local or solicited systemic AEs and vital signs will be documented in the eCRF by study-site personnel following this observation period.

A subject diary, thermometer, and ruler will be provided to measure and record body temperature and solicited local and systemic AEs for 7 days post-vaccination.

RTI Symptoms Forms will be distributed to each subject's parent/legal guardian or caregiver. See Section 9.2.2 for details on completion of the RTI Symptoms Form.

Visits 5 and 8: Day 29/Vaccination 2 and Day 57/Vaccination 3

After verification of selected eligibility criteria,^a abbreviated physical examination (at the discretion of the investigator) and measurement of vital signs, length and weight will be performed for all subjects pre-vaccination. Before the second or third vaccination, the investigator must check for any symptoms of an acute illness. In such a situation, the subject may be vaccinated up to, and no later than 10 days after the scheduled vaccination, or be withdrawn at

^x Exclusion criterion 1, 2, 3, 4, 6, 7, 9, 10, 11, 13, 14, 15, 16, 17, and 18.

^y If within the screening window. Otherwise, rescreening is required.

the discretion of the investigator and after consultation with the sponsor. In the event of an ongoing AE or other situation precluding subject vaccination within 10 days, subjects may be vaccinated beyond the 10-day window at the discretion of the sponsor.

Administration of study vaccine.

Subjects will be closely observed for a minimum of 30 minutes (or 60 minutes, depending on local or study-site requirements) post-vaccination to monitor for the development of any acute reactions, or longer if deemed necessary by the investigator. Any unsolicited, solicited local or solicited systemic AEs and vital signs will be documented in the eCRF by study-site personnel following this observation period.

A subject diary, thermometer, and ruler will be provided to measure and record body temperature and solicited local and systemic AEs for 7 days post-vaccination.

RTI Symptoms Forms will be distributed to each subject's parent/legal guardian or caregiver.

9.1.3.2.2. Post-vaccination Follow-Up

9.1.3.2.2.1. Post-first, Post-second and Post-third Vaccination Follow-Up

Visits 3 and 4 (3 and 7 Days Post-first Vaccination), Visits 6 and 7 (3 and 7 Days Post-second Vaccination) and Visits 9 and 10 (3 and 7 Days Post-third Vaccination)

Visits 3, 6 and 9 at 3 days post-vaccination will be a telephone call to check subject diaries and to collect safety information (solicited and unsolicited AEs, SAEs, concomitant medications, and RTIs).

Visits 4, 7 and 10 at 7 days post-vaccination will include an abbreviated physical examination (at the discretion of the investigator), vital signs measurement, and recording of any (serious) AEs, concomitant medications and RTIs. The subject diary will be reviewed and collected. If Visit 4 occurs before the end of Day 8, Visit 7 occurs before the end of Day 36 or Visit 10 occurs before the end of Day 64 (ie, before the end of the post-vaccination diary period), review of the diary will still take place, but the diary will be returned by the subject's parent/guardian or caregiver at the next visit (ie, Visit 5, Visit 8 or Visit 11, respectively).

A blood sample for immunogenicity assessments will be collected from all subjects 7 days post-first vaccination.

Note: If any subject comes in earlier than Day 8 for Visit 4, Day 36 for Visit 7 or Day 64 for Visit 10 (allowed windows are -1/+3, ± 2 days, and ± 2 days, respectively), a subsequent phone call will be made at the end of the diary period to collect diary card information recorded between the actual visit and the end of the diary period (ie, Day 8, Day 36 or Day 64, respectively).

9.1.3.2.2.2. Post-last Vaccination Follow-Up

Visits 11 and 12 (28 Days and 6 Months Post-third Vaccination)

Visits 11 and 12 will include an abbreviated physical examination including vital signs measurement (at the discretion of the investigator), measurement of length and weight, recording of unsolicited AEs (Visit 11 only), any RTIs, any SAEs, concomitant medications, and any MA-RTIs.

Samples for immunogenicity assessments will be collected at Visit 11.

A nasal sample will be collected 28 days post-final vaccination from all subjects at Visit 11.

Parents/legal guardians or caregivers (where allowed by local regulations) will be invited to complete an Institutional Review Board/Independent Ethics Committee (IRB/IEC) approved Participant Experience Survey at Visit 12 (See Section 9.2.4).

9.1.3.2.3. End of RSV Season Visit

The end of season visit will include an abbreviated physical examination including vital signs measurement (at the discretion of the investigator), measurement of length and weight, any RTIs, any SAEs, concomitant medications, and any MA-RTIs.

Samples for immunogenicity (humoral) assessments will be collected.

Subjects' parents/legal guardians will be informed of the timing of the start and end of the RSV season in accordance with the country/region-specific RSV local surveillance system (if available) or the local surveillance at the site (standard of care assessments, if available).

9.1.3.2.4. Early Withdrawal: Early Exit Visit

For those subjects who are unable to continue participation in the study up to the visit at the end of the RSV season, but for whom consent is not withdrawn, an early exit visit will be conducted as soon as possible. In the event of early withdrawal from the study, all procedures required at Visit 12 will be performed (see Section 9.1.3.2.2.2). Samples for immunogenicity assessments will be collected at the early exit visit as follows: if the early exit visit is before Day 85, 4 mL for cellular assessments and 1 mL for humoral assessments will be collected; if the early exit visit is after Day 85, only 2 mL for humoral assessments will be collected.

If the early exit visit occurs within 7 days of the last vaccination, solicited AEs will be recorded; if the early exit visit occurs within 28 days of the last vaccination, unsolicited AEs will be recorded.

Note: Subjects for whom consent is withdrawn only for blood draws may remain in the study and continue to receive study vaccine and undergo safety follow-up.

9.1.3.3. Safety Follow-up

Each subject's parent/legal guardian or caregiver will be contacted by telephone (or other communication, or clinic visit) through 2 RSV seasons after the first dose, including during the vaccination phase and safety follow-up phase (every 30 days \pm 7 days outside of the RSV season, and every 14 days \pm 3 days within the RSV season, unless the timing coincides with a visit).

During the RSV season, these calls will remind the parents/legal guardians or caregivers to contact the site if their child develops any symptoms of RTI/otitis media; during and outside the RSV season, these calls will be to check for any SAEs and associated concomitant medications, any MA-RTIs/medically-attended otitis media cases, and any subsequent medical care that may have been sought, since the previous visit or telephone contact (this includes contacts with subjects who received at least one dose of study vaccine but withdrew from further dosing).

The follow-up phase will include all subjects who received at least one dose of study vaccine.

9.2. Study Evaluations

9.2.1. Immunogenicity

Venous blood samples will be collected for the determination of humoral and cellular responses according to the [Time and Events Schedule](#). Sample collection and processing will be performed by the staff at clinical sites according to current and approved Standard Operating Procedures.

The humoral and cellular immunogenicity assays that may be used in this study (as available and applicable) are summarized in [Table 5](#) and [Table 6](#), respectively.

Immunogenicity samples will be prioritized as outlined in the Laboratory Manual.

Table 5: Summary of Immunogenicity Assays (Humoral)

Assay	Purpose
Secondary endpoints	
RSV neutralization A strain	Analysis of neutralizing antibodies to an A strain
F protein antibodies (ELISA; pre-F and/or post-F)	Analysis of antibodies binding to RSV F protein in pre-fusion and/or post-fusion form
Exploratory endpoints	
RSV strain cross-neutralization	Analysis of cross-neutralizing antibodies to B and/or a different A strain(s)
F protein antibody specificity characterization	Pre-F and post-F specificity by binding or functional assays as ELISA, and/or competition ELISA, epitope mapping, and functional VNAs
Nasal Ig antibodies to RSV F protein	Analysis includes, but not limited to, IgA or IgG antibodies to RSV pre-F and/or post-F
G and/or N protein antibodies (ELISA)	Analysis of antibodies binding to RSV G and/or N protein
Adenovirus neutralization assay	Analysis of neutralizing antibodies to adenovirus
Functional and molecular antibody characterization	Analysis of antibody characteristics including, but not limited to, ADCC, ADCP, avidity, other respiratory viral neutralizing or binding assays, Ig isotype, functional VNAs to other respiratory viruses, and antibody assessments

ADCC = antibody-dependent cell-mediated cytotoxicity; ADCP = antibody-dependent cellular phagocytosis; ELISA = enzyme-linked immunosorbent assay; F = fusion; Ig = immunoglobulin; RSV = respiratory syncytial virus; VNA = virus neutralizing antibody

Table 6: Summary of Immunogenicity Assays (Cellular)

Assay	Purpose
Secondary endpoints	
Flow cytometry (ICS)	Analysis of T-cell responses to RSV F protein peptides for Th1/Th2 subtyping
Exploratory endpoints	
ICS	Analysis of T-cell responses to RSV F protein peptide-stimulated PBMC (including, but not limited to, CD4 ⁺ /CD8 ⁺ , IL-2, IFN- γ , TNF- α , activation markers and memory)
Cytokine analysis	Analysis of secreted cytokines (eg, IFN- γ , IL-2, IL-4, IL-5, IL-13, and TNF- α) in RSV F peptide-stimulated PBMC supernatant, including, but not limited to, measurement of Th1/Th2 cytokine balance
IFN- γ ELISpot	T-cell IFN- γ responses to RSV F protein peptides

ELISpot = enzyme-linked immunospot; F = fusion; ICS = intracellular cytokine staining; IFN- γ = interferon gamma; IL = interleukin; PBMC = peripheral blood mononuclear cell; Th = T-helper (cell); RSV = respiratory syncytial virus; TNF- α = tumor necrosis factor alpha

Note: Cytokine analysis for Th1/Th2 profiling will be done if no ICS data can be generated due to insufficient PBMCs for ICS assay.

In addition to RT-PCR performed on RTI nasal samples, any immunogenicity blood sample collected from all subjects may also be assayed by serology (eg, ELISA specific to RSV protein G and/or N as available and applicable) to confirm exposure to RSV at the end of the season if the sample volumes allow.

Instructions for collection, handling, storage, and shipment of blood and nasal samples for immunogenicity assay can be found in the Laboratory Manual that will be provided. Collection, handling, storage, and shipment of blood and nasal samples to the central laboratory must be under the specified, and where applicable, controlled temperature conditions as indicated in the Laboratory Manual.

9.2.2. RTI Procedures

All RTIs and otitis media cases will be collected during the RSV season^z. Outside the RSV season, only MA-RTIs (including severe LRTIs; see Section 11.3.1.1) and medically-attended otitis media cases will be collected.

During the RSV season, the subject's parent/legal guardian or caregiver should record any signs and symptoms of RTI (eg, runny nose, fever, severe cough, wheezing, rapid breathing, difficulty breathing) or otitis media on a daily basis using a specific RTI Symptoms Form, starting on the first day their child experiences symptoms. Outside the RSV season, parents/guardians or caregivers should likewise record signs and symptoms of RTI or otitis media on a daily basis using the RTI Symptoms Form as soon as possible for any MA-RTI or medically-attended otitis media case until resolution of symptoms. A new form should be completed each day the subject has symptoms, including the day on which the symptoms resolve. RTI Symptoms Forms will be distributed at the timepoints as indicated in the [Time and Events Schedule](#). Completed RTI forms can either be mailed to the site or brought to the site at the next visit.

^z *Note:* The RTI procedures also apply to all otitis media cases.

In the event of an RTI, MA-RTI, or (medically-attended) otitis media, parents/legal guardians or caregivers should contact the site. Parents/legal guardians or caregivers will themselves be contacted periodically during the study. During the RSV season, these calls are to remind them to complete the RTI Symptoms Form in the event of any signs or symptoms of RTI or otitis media, and to contact the site at the time of symptom onset; during and outside the RSV season, these calls will check for SAEs and associated concomitant medications, MA-RTIs, medically-attended otitis media cases, and any subsequent medical care that may have been sought, since the previous visit or telephone contact (this includes contacts with subjects who received at least one dose of study vaccine but withdrew from further dosing).

During the season, and where possible outside the season (for MA-RTIs, including severe LRTIs or for medically-attended otitis media cases), site staff will conduct a physical examination (with vital signs, including oxygen saturation), and collect nasal samples, preferably within 72 hours after onset of symptoms. For suspected severe RTI cases, nasal swabs should be shipped on the day of collection to enable timely assessment of samples for the presence of RSV infection by central laboratory RT-PCR. To evaluate the safety of the Ad26.RSV.preF vaccine, nasal samples may also be assessed for the presence of other respiratory pathogens. The actual dates and times of sample collection and physical examination data must be recorded in the eCRF, preferably within 24 hours of sample collection. Any suspected case of severe RSV-LRTI should be recorded in the eCRF within 24 hours of knowledge of the event. (*Note*: Nasal samples will not be collected if less than 7 days after the previous sample collection.) *Note*: A nasal swab for RSV RT-PCR testing will also be collected from any subject with otitis media (as recorded on the RTI Symptoms Form) during the study, independent of other RTI symptoms.

For all RTIs, every effort should be made to collect data on the clinical course of infection including information on oxygenation status, supplemental oxygen requirements and specific drug treatments, as well as other concurrent respiratory illness present at the time of the diagnosis of the event and up to symptom resolution.

In all RTI or otitis media cases where results from the physical examination during the RTI site visit conclude that the RTI is not severe, and the RTI episode is still ongoing, a follow-up phone call (or other communication) to the parents/legal guardians or caregivers will be made once every 2 working days (± 1 day) until symptom resolution. In the event of a worsening RTI, a follow-up RTI visit will be scheduled. (*Note*: In the event of a worsening RTI, a repeat nasal sample may be collected if less than 7 days after the previous sample collection at the discretion of the investigator.) The data from this second RTI visit must be recorded in a separate eCRF page and will have a separate conclusion (severe/non-severe). Further follow-up visits to assess additional reported worsening of an RTI episode may be scheduled at the discretion of the investigator.

Signs and symptoms of RTI or otitis media recorded by the subject's parent/legal guardian on the RTI Symptoms Form will be transferred onto the applicable RTI symptoms page in the eCRF, preferably within 24 hours of receipt of the form.

Note: RTI procedures (completion of the RTI symptoms form at home, and an RTI visit to the site with associated procedures, including nasal sampling) are not applicable for a non-medically-attended RTI that occurs outside the season, including those that started before the RSV season and continue into the season without worsening of symptoms.

[figure not shown]
Any RTI or otitis media case that is not due to RSV infection will be reported as an AE if it occurs between the time of any study vaccination through the following 28 days. During the study, any RTI or case of otitis media fulfilling the criterion of an SAE will be reported to the sponsor (and, when appropriate, extended to Regulatory Agencies). Any RTI or case of otitis media reported as an (S)AE that is found to be positive for RSV will be excluded from the analyses of (S)AEs. However, the case will remain in the clinical database and will be tabulated separately in the clinical study report.

Any MA-RTI (including any severe LRTI) or (medically-attended) otitis media case which occurs between screening and Day 1 will be recorded on the Medical History page of the eCRF (RTI visit and RTI Symptoms Form completion is not required for these events prior to the first vaccination).

An overview of the RTI procedures is provided in [Figure 2](#) below. *Note:* The RTI procedures also apply to all otitis media cases.

Any parent/legal guardian or caregiver who seeks medical attention for their child due to an RTI or otitis media should make the attending healthcare professional aware that their child is taking part in an RSV vaccine study. Each parent/legal guardian or caregiver will be given a wallet card with key study information and study-site contact details (see Section [12.3.1](#)). These details should be shared with the attending healthcare professional.

Figure 2: Procedures in the Event of a Respiratory Tract Infection or Otitis Media Case

^a Severe LRTIs are a subset of MA-RTIs. *Note:* Any MA-RTI (including any severe LRTI) which occurs between screening and Day 1 will be recorded on the Medical History page of the eCRF.

^b During the RSV season, subjects’ parents/guardians or caregivers should record signs and symptoms of RTI using the RTI Symptoms Form on a daily basis starting on the first day they experience symptoms, including the day on which symptoms resolve. Outside the RSV season, parents/guardians or caregivers should likewise record signs and symptoms of RTI on a daily basis using the RTI Symptoms Form as soon as possible for any MA-RTI until resolution of symptoms.

Subjects’ parents/guardians or caregivers will be informed of the timing of the start and end of the RSV season in accordance with the country/region-specific RSV local surveillance system.

^c Any RTI that is not due to RSV infection will be reported as an AE if it occurs between the time of any study vaccination through the following 28 days. Any RTI recorded as an AE in the eCRF will be excluded from any AE analysis if the central laboratory RT-PCR is subsequently found to be positive for RSV. RTIs arising from RSV infection will not be reported as (S)AEs in the CSR as they are endpoints of the study but will be tabulated separately.

^d During the study, any RTI or case of otitis media fulfilling the criterion of an SAE will be reported to the sponsor (and, when appropriate, extended to Regulatory Agencies). Any RTI or case of otitis media reported as an (S)AE that is found to be positive for RSV will be excluded from the analyses of (S)AEs. However, the case will remain in the clinical database and will be tabulated separately in the clinical study report.

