2. OBJECTIVES, ENDPOINTS, AND HYPOTHESIS

2.1. Objectives and Endpoints

2.1.1. Objectives

Primary Objective

The primary objective is:

- To assess the safety and reactogenicity of an intramuscular regimen of 3 doses of 2.5×10^{10} vp of Ad26.RSV.preF in RSV-seronegative toddlers aged 12 to 24 months.

Secondary Objectives

The secondary objectives are:

- To assess the humoral and cellular immune responses elicited by Ad26.RSV.preF as measured by virus neutralizing antibodies (VNAs), F protein binding antibodies (pre-F and/or post-F), and Th1/Th2 subtyping.
- To monitor for severe RSV-LRTI as a preliminary indication of ERD.

Exploratory Objectives

The exploratory objectives are:

- To further assess the humoral and cellular immune responses elicited by Ad26.RSV.preF. The assays to be used can include, but may not be limited to, RSV strain cross-neutralization, RSV F protein antibody specificity characterization, RSV G and/or N protein binding antibodies, adenovirus neutralization assay, functional and molecular antibody characterization (eg, avidity and antibody isotyping) and antibody sequencing if feasible, and evaluation of cellular immune response (IFN- γ enzyme-linked immunospot [ELISpot] assay, intracellular cytokine staining [ICS], cytokine analysis).
- To assess RSV infection rates (symptomatic and asymptomatic) in Ad26.RSV.preF and control subjects.
- To assess symptomatic RSV infection rates in Ad26.RSV.preF and control subjects.
- To assess symptoms of respiratory illness via the Respiratory Tract Infection (RTI) Symptoms Form.

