2.1.2. Endpoints

Primary Endpoints – Safety and Reactogenicity

- Solicited local and systemic AEs for 7 days after each vaccination.
- Unsolicited AEs for 28 days after each vaccination.
- SAEs from first dose administration to the end of the study.

Secondary Endpoints – Immune Responses

The analysis of the immunogenicity of the vaccine regimens will include the characterization of both humoral and cellular responses. The focus of the immunogenicity analysis will be on VNAs, F protein antibodies (pre-F and/or post-F), and Th1/Th2 cytokine profile response.

Humoral Immune Response

- RSV neutralization A strain
Analysis of neutralizing antibodies to an A strain.
- F protein antibodies (enzyme-linked immunosorbent assay [ELISA]; pre- and/or post-F)
Analysis of antibodies binding to RSV F protein in pre-fusion and/or post-fusion form.

Cell-mediated Immune Response

- Flow cytometry (ICS)*
Analysis of T-cell responses to RSV F protein peptides for Th1/Th2 subtyping.

** Cytokine analysis for Th1/Th2 profiling will be done if no ICS can be generated due to an insufficient number of peripheral blood mononuclear cells (PBMCs) for ICS assay (see the Exploratory Endpoints below).*

Secondary Endpoints – RSV Infection

- Severe RSV-LRTI
Severe RSV-LRTI will be defined as the presence of severe LRTI as assessed by the Clinical Endpoint Committee (CEC; See Section 11.3.1.2), and confirmation of RSV infection from a nasal (mid-turbinate or nasopharyngeal) sample using independent reverse transcriptase polymerase chain reaction (RT-PCR) by a central laboratory. If no central laboratory RT-PCR result is available, a positive test result for RSV from a local laboratory (if available) could be used to confirm RSV infection upon evaluation by the CEC.

Exploratory Endpoints – Immune Responses

Exploratory analyses may be performed to evaluate the vaccine-elicited immune responses further. These can include, but may not be limited to, the following assays (as available and applicable):

Humoral Immune Response

- RSV cross-neutralization of B and/or other A strain(s)
Assessment of the strain cross-neutralizing capacity of the vaccine-induced immune response.
- F protein antibody specificity characterization
Assessment of pre-F and post-F specificity by binding or functional assays as ELISA, and/or competition ELISA, epitope mapping, and functional VNAs.
- Nasal immunoglobulin antibodies to RSV F protein
Analysis of IgA or IgG antibodies to RSV pre-F and/or post-F

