11.7. Safety Analyses

No formal statistical testing of safety data is planned. All safety data will be analyzed descriptively by regimen.

Adverse Events

The verbatim terms used in the eCRF by investigators to identify AEs will be coded using the Medical Dictionary for Regulatory Activities (MedDRA). All reported AEs with onset after vaccination up to 28 days post-vaccination, and SAEs from first dose administration onwards, will be included in the analysis. For each AE, the percentage of subjects who experience at least 1 occurrence of the given event will be summarized by group.

Summaries, listings, datasets, or subject narratives may be provided, as appropriate, for those subjects who die, who discontinue vaccine due to an AE, or who experience a severe AE or an SAE.

Summaries and/or listings may be provided separately for AEs with onset outside the above defined time frame (eg, beyond 28 days post-vaccination) and that were reported pre-dose at the moment of subsequent vaccinations for studies using multiple doses.

Solicited local (at injection site) and systemic AEs will be summarized descriptively. The overall frequencies per vaccine group as well as frequencies according to severity and duration will be calculated for solicited AEs. In addition, the number and percentages of subjects with at least one solicited local (at injection site) or systemic AE will be presented. Frequencies of unsolicited AEs, separately for all and vaccination-related only, will be presented by System Organ Class and preferred term. *Note*: Frequencies of post-dose 3 AEs in the control group will be presented separately for Nimenrix and placebo.

Any RTI or otitis media case recorded as an AE in the eCRF that is subsequently found to be RSV positive by RT-PCR (central laboratory or based on CEC assessment if available) will be excluded from the safety analysis and tabulated separately.

Vital Signs

A tabulation of the distribution of temperatures per half degree intervals will be provided. For heart rate and respiratory rate, the percentage of subjects with values beyond clinically relevant limits will be summarized. *Note:* Vital signs data post-dose 3 in the control group will be presented separately for Nimenrix and placebo.

Physical Examination

Physical examination abnormalities will be listed.

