11.9.2. Independent Data Monitoring Committee (IDMC)

An IDMC will be established to review safety data, and as needed on an ad hoc basis to ensure the continuing safety of the subjects enrolled in this study. The IDMC will convene to discuss any situation that meets a study vaccination pausing rule (see Section 11.10).

The presence of severe LRTI and the occurrence of RSV infection will be determined by the CEC, a separate committee (see Section 11.9.1).

The IDMC will monitor severe RSV-LRTI as assessed by the CEC according to the rule described in Section 11.3.1.3 and further detailed in the IDMC charter.

The IDMC will consist of members independent of the sponsor, including at least one medical expert in the relevant therapeutic area and at least one statistician. An immunologist may be included on an ad hoc basis, as needed. The IDMC responsibilities, authorities, and procedures will be documented in its charter. An external statistician independent of the sponsor and not involved in the interim, primary, and final analyses of the study will prepare the data and perform all analyses for review by the IDMC.

In any case(s) under review, the IDMC will review unblinded data.

Details on the intervals of the safety evaluations will be provided in the IDMC charter.

Safety data from the interim and primary analyses will be shared with the IDMC.

If any question arises related to safety, the IDMC will be convened.

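### The primary endpoint is every SAE from first dose onward, but its analysis drops RSV-positive respiratory and otitis media SAEs, and the RSV endpoints do not fully replace them

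*Protocol*

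**What the plan says.** **Endpoint.** Protocol 2.1.2 lists as a primary endpoint "SAEs from first dose administration to the end of the study". SAP 4.1.1 repeats it. Neither place makes an exception for RSV.

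**Exclusion.** Protocol 9.2.2 says that an RTI or otitis media case reported as an (S)AE that "is found to be positive for RSV will be excluded from the analyses of (S)AEs". The Synopsis and 12.1.1 carry the same rule. Section 11.7 first states that SAEs from first dose onward enter the analysis. It then says that an RTI or otitis media case recorded as an AE and later found RSV positive "will be excluded from the safety analysis and tabulated separately".

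**Reason and safeguards.** The footnotes to Figure 2 in 9.2.2 explain that RSV-caused RTIs "will not be reported as (S)AEs in the CSR as they are endpoints of the study but will be tabulated separately". Section 9.2.2 adds: "However, the case will remain in the clinical database and will be tabulated separately in the clinical study report". Expedited reporting is unaffected, because "any RTI or case of otitis media fulfilling the criterion of an SAE will be reported to the sponsor".

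**Where enhanced disease is assessed.** Section 2.1.1 has the secondary objective "To monitor for severe RSV-LRTI as a preliminary indication of ERD". Section 11.9.2 states: "The IDMC will monitor severe RSV-LRTI as assessed by the CEC according to the rule".

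**SAP.** It covers IDMC analyses only. Sections 4 and 4.1.1 present SAEs for all phases and do not mention the RSV exclusion.

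**The concern.** A primary endpoint should be analysed as it is defined. Here a subset of SAEs is removed on the basis of an RSV test taken after randomization. The vaccine is meant to alter RSV infection and, in the feared scenario, its severity, so the removal need not be balanced between groups. If the vaccine worsened RSV disease, the rule would take more events out of the vaccine column. If it protected, the rule would take more out of the control column.

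The removed events bear on the hazard described in Protocol 3.3.4. That section describes enhanced disease after the formalin-inactivated vaccine through hospitalizations (16 of 31 vaccinees, 1 of 40 controls) and two deaths among vaccinees. Hospitalization and death are both SAE criteria in 12.1.1. Read literally, a fatal RSV-positive RTI would be absent from the SAE analysis, although 11.10 sends every death to the IDMC.

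At stake is whether the SAE table can be read as what the endpoint says it is, and whether every removed event reappears in an equally visible place.

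**Working it through.** **1. Does anything else depend on the exclusion?** The related figure in the plan is in 11.2: at least 80% power to halt enrollment if severe RSV-LRTI incidence is about 25% with vaccine and 1% in controls.

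- Inputs: 18 per group (Table 4); rates 25% and 1% (11.2); Wilson-score limits for a difference in proportions and a trigger of 2 events (11.3.1.3).
- Method: sum the products of the two binomial probabilities over all outcomes with at least 2 events in total, a lower one-sided 95% limit above 0 and an upper one-sided 95% limit of at least 10%.
- Result: 79.7% at 25% and 81.9% at 26%, which agrees with the stated figure to rounding. This takes the limits literally, so 3 versus 0 counts as a halt (lower limit +0.33%). The worked example in 11.3.1.3 says otherwise, but that is a separate matter.
- The rule uses severe RSV-LRTI events and not the SAE table, so the power is the same with or without the exclusion.

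**2. What the exclusion does to the SAE table.** Assume, for illustration only, 4 severe RSV-LRTIs with vaccine and 0 in controls, all meeting SAE criteria.

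- Contribution to the SAE table as planned: 0/18 versus 0/18.
- Contribution under the endpoint as defined: 4/18 = 22.2% versus 0/18.
- Severe RSV-LRTI endpoint, either way: 4/18 versus 0/18. With z = 1.645, the Wilson limits are 0.104 and 0.413 for 4/18, and 0 and 0.131 for 0/18.
 - Lower limit: 0.222 − √[(0.222 − 0.104)² + 0.131²] = +4.6%.
 - Upper limit: 0.222 + (0.413 − 0.222) = 41.3%.
 - The halt criterion is met, provided all four children are in the set analysed.

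**3. Do the other routes catch every removed SAE?** Setting the sections side by side gives five gaps.

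- *Otitis media.* Section 9.2.2 requires a swab for otitis media even without RTI symptoms, and 12.1.1 treats RSV-caused otitis media as a study endpoint. The endpoint list in 11.3.1 contains only RTI and LRTI endpoints. A serious RSV-positive otitis media without RTI belongs to none of them. It might enter the RSV infection summary in 11.6, but as an infection and not as a serious event.
- *Hospitalized RSV-RTI below the severe definition.* Severe status needs an RTI the investigator considers severe, followed by committee assessment focused on oximetry and chest indrawing (11.3.1.2). Other admissions count as RSV MA-RTI (11.3.2), which is exploratory.
- *Analysis set.* Safety uses FA. RSV infection is primarily analysed on mITT, which drops children with a Day 8 anamnestic response (11.1). An RSV-positive SAE in such a child is outside both the SAE analysis and the primary RSV analysis, and appears only in the separate tabulation.
- *Criterion for RSV positive.* The main text of 9.2.2 names no test. The Figure 2 footnote on AEs and the AE paragraph of 12.1.1 use central-laboratory RT-PCR. Sections 11.6 and 11.7 use the central laboratory or committee assessment. A case positive only at a local laboratory could be kept or removed.
- *Missing result.* Under 11.3.1.2 an RTI with no conclusive test is not RSV-related, so it stays in the SAE analysis. Two similar admissions can be handled differently because one child was not swabbed.

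The layout of the separate tabulation (by group, seriousness and analysis set) is not specified, so it cannot be assumed to close these gaps.

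**The case against.** The strongest reply is that this is an open, reasoned presentation choice. Section 12.1.1 states the exception beside the SAE definition, with its rationale. Amendment 5 lists the clarification among changes following a national health authority's requests. Counting an event under its own endpoint avoids showing it twice. No hypothesis is tested (2.2) and safety is descriptive (11.7), so there is no formal comparison to bias. A reader of the study report would have both tables.

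Much of this stands. There is no type I error or power consequence, and nothing is hidden. It does not remove the mismatch: 2.1.2 defines the endpoint without the exception, and 11.7 both includes SAEs from first dose and excludes some of them. A descriptive table can still mislead if its contents depend on a post-randomization result, and the second table is neither specified nor aligned to the same analysis set.

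A reader might also infer that the trial fails to count enhanced disease. The documents do not support that. A blinded committee assesses severe RSV-LRTI, an unblinded IDMC applies a rule that can halt enrollment, hospital admissions fall under RSV MA-RTI, and serious cases still go to the sponsor.

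A reader might further infer that IDMC and study-report SAE counts will differ. That is not shown. The SAP is silent on the exclusion rather than contrary to it, and it plans one IDMC analysis, at Day 8 after the first dose in the first 12 toddlers. Counts could differ, because the IDMC also receives safety data from later analyses and the SAP guides any further requests.

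**Conclusion.** The point holds as a mismatch between the definition of a primary endpoint and its analysis, together with incomplete coverage by the routes meant to replace it. It should be corrected, but it is not an omission of the key safety signal.

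Its numerical size cannot be fixed in advance, because the documents give no expected rate of RSV-positive SAEs. The 4/18 versus 0/18 illustration shows the mechanism and assumes that every severe case is also an SAE. It would be tempting to take 0.25 × 18 = 4.5 or 16/31 × 18 = 9.3 vaccinees as the expected loss. Neither is supported. The 25% is a severe RSV-LRTI incidence at which the halting rule's power is stated, and the severe definition does not require hospitalization. The 16/31 comes from a different vaccine whose risk was highest under 6 months of age, whereas this trial enrolls at 12 to 24 months.

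The conclusion assumes that the exclusion is applied as written in 9.2.2 and 12.1.1, and that the separate tabulation is no more detailed than the documents state.

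**What to change.** - On the FA set, make the primary SAE summary a table of all SAEs by group, whatever the RSV result.
- Add a second row with RSV-positive RTI and otitis media cases removed, which keeps the sponsor's preferred view.
- Do the same for unsolicited AEs in the 28 days after each vaccination.
- Keep the separate RSV tabulation, and specify it by group, seriousness and analysis set so that otitis media cases and children outside mITT are visible.
- State one inclusion rule and one criterion for RSV positive, and use them in Protocol 2.1.2, 9.2.2, 11.6, 11.7 and 12.1.1 and in SAP 4 and 4.1.1.

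The cost is one extra row per table and some wording. RSV cases will appear both in the SAE table and among the RSV endpoints, so a footnote should say so. Data collection, expedited reporting and the IDMC rule do not change.
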